1.2.4 Exploratory Efficacy Objective

The objective of exploratory efficacy analysis is to demonstrate the ability to measure clinical effect.

1.2.4.1 Efficacy Endpoints

Exploratory efficacy endpoints will be evaluated from the time of lucinactant for inhalation initiation until the completion of Study Day 7 (non-hypothesis testing) and will include the following:

1. Incidence of BPD
2. Rate of survival without BPD at 36 weeks PMA
3. Worsening of respiratory status

4. Technical performance of the ADS

- The efficacy of the device delivery of lucinactant for inhalation will be characterized indirectly through the subject's response to treatment and solicited feedback from the principal investigators (PIs) and relevant site-based study staff.

5. Physiological parameters (eg, FiO_2 , PCO_2)

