1 INTRODUCTION

The purpose of this study is to evaluate the safety and tolerability of a sequential, escalating dose of lucinactant for inhalation (a non-invasive, investigational drug-device combination product) administered in preterm neonates 26 weeks to 28 completed weeks (28 weeks 6 days) post-menstrual age (PMA) with respiratory distress syndrome (RDS) treated with nasal continuous positive airway pressure (nCPAP), in comparison with nCPAP alone.

Non-invasive surfactant delivery potentially addresses an unmet medical need by providing a means to deliver surfactant to preterm neonates with RDS treated with nCPAP, thereby providing surfactant therapy early in the disease course while avoiding the complications associated with endotracheal intubation for surfactant delivery.

This phase 2a study is designed to assess the safety and tolerability of a novel surfactant replacement therapy (SRT), lucinactant for inhalation, administered at select doses in preterm infants 26 to 28 completed weeks PMA. A similar study, Protocol 03-CL-1201, in preterm neonates 29 to 34 completed weeks PMA, was conducted first to establish that lucinactant for inhalation is generally safety and well tolerated. Similar to this study (03-CL-1401), Protocol 03-CL-1201 evaluated lucinactant for inhalation in a dose-escalation manner up to 75 mg total phospholipids (TPL)/kg, with a currently ongoing study extension in that population up to 150 mg TPL/kg. Findings from these two studies (03-CL-1201 and 03-CL-1401) will contribute to the development and design of future investigations of this novel drug/device combination product.

All study procedures and assessments are to be conducted in accordance with local and regional regulatory requirements, institutional review board (IRB)/independent ethics committee (IEC) requirements, International Conference on Harmonisation Good Clinical Practices (ICH GCP) Guidelines, and local institutional practices. In addition, the study procedures and assessments are designed to mimic those of Protocol 03-CL-1201.

Definitions of study terms are provided in [Appendix 1](#).

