3.4.1 Efficacy Endpoints

Exploratory efficacy endpoints will be evaluated from the time of lucinactant for inhalation initiation until study completion (non-hypothesis testing) and will include the following:

1. Incidence of BPD
2. Rate of survival without BPD at 36 weeks PMA or upon discharge
3. Worsening of respiratory status (Section 7.5)
4. Technical performance of the ADS
 - The efficacy of the device delivery of lucinactant for inhalation will be characterized indirectly through the subject's response to treatment and solicited feedback from the PIs and relevant site-based study staff.
5. Physiological parameters (eg, FiO₂, PCO₂)

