- AEs and ADEs (including peri-dosing events and nasal excoriations)
- Air leak (especially pneumothorax and pneumomediastinum)
- Survival
- Use of respiratory support and supplemental oxygen
- Complications of prematurity
- Assessments of the following:
 - a) Arterial carbon dioxide (PCO₂)
 - b) Serum electrolyte measurements
 - c) Vital signs
 - d) Gastric liquid volume
 - e) Oxygen saturations (SpO₂)
- Chest radiography prior to intubation, if such a procedure does not delay or compromise the emergent care of the subject

A peri-dosing event is defined as an adverse event with an onset time ≤ 2 hours from the time of initiating administration of lucinactant for inhalation

Efficacy endpoints (exploratory objective) in the study include:

- Incidence of bronchopulmonary dysplasia (BPD) at 36 weeks PMA
- Rate of survival without BPD at 36 weeks PMA
- Technical performance of the ADS
- Worsening respiratory status either during or after exposure to lucinactant for inhalation
- Physiological parameters (eg, FiO₂, PCO₂)

The statistical analysis of both the primary and secondary safety and tolerability objectives will be based on all randomized preterm neonates in the study. In addition, data from all evaluable preterm neonates will be analyzed for efficacy signals as an exploratory endpoint. As this is an open-label study with no hypothesis testing, no adjustments for *p*-values are required or employed.

TABLE OF CONTENTS

EXECUTIVE SUMMARY	3
1 OVERVIEW.....	9
1.1 BACKGROUND.....	9
1.1.1 Treatment of Neonatal Respiratory Distress Syndrome	9
1.1.2 Development of Aerosolized Device for Lucinactant Delivery	10
1.2 OBJECTIVES	11
1.2.1 Primary Objective	11
1.2.2 Secondary Objective	11
1.2.3 Safety Evaluations	11
1.2.4 Exploratory Efficacy Objective	12
1.3 HYPOTHESES.....	13
2 INVESTIGATIONAL PLAN	14
2.1 STUDY POPULATION	14
2.1.1 Inclusion criteria	14
2.1.2 Exclusion Criteria	14
2.2 STUDY DESIGN AND RANDOMIZATION.....	15
2.2.1 Treatment Groups	16
2.2.2 Repeat Dosing	16
2.2.3 Sample Size Justification	17
2.2.4 Study Schedule	18
3 STUDY SUBJECT CHARACTERISTICS.....	19
3.1 DEMOGRAPHICS AND BASELINE CHARACTERISTICS	19
3.1.1 Demographics	19
3.1.2 Birth and Maternal History	19
3.2 SUBJECT DISPOSITION	19
3.3 STUDY AND CONCOMITANT MEDICATION.....	20
3.3.1 Compliance	20
3.3.2 Number of Doses	20
3.3.3 Previous and Concomitant Medication	20

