4.2 EFFICACY ENDPOINTS

Exploratory efficacy endpoints will be evaluated from the time of lucinactant for inhalation initiation until study completion (non-hypothesis testing) and will include the following:

- Intubation and surfactant administration
- Onset/incidence of bronchopulmonary dysplasia (BPD)
- Survival without BPD at 36 weeks PMA
- Worsening of respiratory status
- Technical performance of the ADS

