4.3 STATISTICAL ANALYSIS

All statistical analyses will use summary statistics to describe all endpoints; no statistical testing will be done. All time points will be measured from time of randomization unless otherwise specified.

Categorical variables will be summarized using frequency and percent. Continuous variables will be summarized using n, mean, SE, SD, median, minimum, and maximum. Summary statistics will be presented by treatment group.

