9.2 WINDOWS FOR VISITS

Accurate clock times will be recorded for each timed event in military time (24-hour clock). Day 1 is the day on which randomization occurs; Day 3 begins at midnight 2 days following randomization and Day 7 will be the sixth day after the day of randomization.

All assessments at pre-specified time points are to be conducted within the windows specified in the protocol. Summary tables will use the pre-specified time points, not the actual times, to summarize the data.

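### The exploratory efficacy window has two different ends in the SAP (Study Day 7 and study completion), and it starts at lucinactant initiation, an event that controls never have

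*SAP*

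**What the plan says.** **End of the window.** SAP 1.2.4.1 reads: "Exploratory efficacy endpoints will be evaluated from the time of lucinactant for inhalation initiation until the completion of Study Day 7 (non-hypothesis testing". Its list includes BPD incidence and "Rate of survival without BPD at 36 weeks PMA". The SAP executive summary places the first of these at the same time: "Incidence of bronchopulmonary dysplasia (BPD) at 36 weeks PMA". SAP 4.2 reads: "Exploratory efficacy endpoints will be evaluated from the time of lucinactant for inhalation initiation until study completion (non-hypothesis testing". Protocol 3.4.1 has the same study-completion end and gives the second BPD item as "Rate of survival without BPD at 36 weeks PMA or upon discharge". SAP 4.3.1 and Table 4.2 summarize both BPD outcomes at 36 weeks.

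**Start of the window.** All three passages begin at the start of lucinactant. SAP 2.2 gives controls nCPAP alone. SAP 4.1 makes the efficacy population every randomized infant. SAP 4.3 says: "All time points will be measured from time of randomization unless otherwise specified". SAP 9.1 sets baseline at the last value before study drug for active infants and at randomization for controls.

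**The concern.** An efficacy window should fit the endpoints it governs and should run over the same period in both arms. The Day 7 version fails the first test for the two BPD endpoints. The lucinactant start fails the second in all three places.

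The start matters more, because it also stands in SAP 4.2, where the efficacy analysis is specified. Protocol 2.1 allows up to 2 hours from randomization to aerosolization. The note to protocol 4.3 requires entry criteria still to be met when therapy starts, and a need for intubation is an exclusion. An active infant intubated in that gap may therefore never be dosed. Protocol 5.7 expects some infants to be randomized but not treated. Under the literal wording such an infant stays in the ITT denominator while the event lies outside the window. A control with the same event at the same time would be counted if the SAP 4.3 default is applied to controls. That difference would favour the active arm.

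**Working it through.** The plan gives no figure to reproduce here. The end can be checked by date arithmetic and the start by comparing passages.

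**End: inputs**
- Gestational age at entry, protocol 1: "preterm neonates 26 weeks to 28 completed weeks (28 weeks 6 days) post-menstrual age (PMA", that is 26w0d (182 days) to 28w6d (202 days).
- BPD time point: 36w0d = 36 × 7 = 252 days.
- Randomization within 20 hours of birth (protocol 5), so 0 or 1 calendar day after birth.
- SAP 9.2: "Day 7 will be the sixth day after the day of randomization".

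**End: calculation**
- Days from birth to 36w0d = 252 − gestational age in days. Born at 26w0d: 252 − 182 = 70. Born at 28w6d: 252 − 202 = 50.
- Study Day 7 = randomization day + 6, which is postnatal day 6 or 7. PMA then lies between 182 + 6 = 188 days (26w6d) and 202 + 7 = 209 days (29w6d).
- Shortfall: smallest 50 − 7 = 43 days, largest 70 − 6 = 64 days.

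No eligible infant reaches 36 weeks by Day 7.

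**End: which endpoints are affected**
- BPD and survival without BPD: Day 7 is too early.
- Worsening respiratory status: categorized up to 7 days after birth (SAP 4.3.2), so it essentially fits.
- FiO₂ and PCO₂: summarized over 72 hours (SAP 6.5.6), so they fit.
- ADS technical performance: tied to dosing (SAP 5), so it fits.
- Intubation and surfactant: not in the 1.2.4.1 list. They enter in SAP 4.2, which ends at study completion.

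**Start: by arm**
- Active, dosed: the window opens at dosing, up to 2 hours after randomization.
- Active, never dosed: the window never opens.
- Control: 32/64 = 50% of infants have no lucinactant initiation. The only available origin is the SAP 4.3 default, randomization.

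**Start: which endpoints are affected**
- Intubation and surfactant (SAP 4.3.3, Tables 4.3 and 4.4): the most exposed, because SAP 4.3.3 sets no window of its own. SAP 4.3 would time an active-arm intubation from randomization, while SAP 4.2 would leave the event out if it came before dosing.
- Worsening: less exposed, because its categories are timed from birth.
- BPD outcomes: a start shifted by up to 2 hours has essentially no effect on status at 36 weeks. The literal wording still gives a never-dosed infant no window.

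**Size of one omitted event:** 1/8 = 12.5 percentage points in a dose group, or 1/32 = 3.1 points in the pooled active arm. The documents do not say how many such events to expect, so this is a size per event and not a forecast.

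**The case against.** The strongest reply is that the analysis sections already settle most of this. SAP 1.2.4.1 belongs to the overview. SAP 4.2, 4.3.1, Table 4.2, the executive summary and protocol 13.1 all point to study completion or 36 weeks. That stands. A reader might infer that the BPD analysis is actually planned at Day 7 and so cannot be done, and the documents do not support that.

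A reader might also infer that the Day 7 cut-off changes the intubation count and time to intubation. It does not govern them, because intubation is absent from the 1.2.4.1 list.

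On the start, it can fairly be said that SAP 4.3 and 9.1 give controls a usable origin, so it would be too strong to say that controls have no start time. It can also be said that early and late worsening are timed from birth and tabulated in the ITT population (Tables 4.1.1 and 4.1.2). Pre-dosing worsening would be lost only if the introductory sentence overrode those definitions. Both replies stand, but they do not remove the problem. The SAP 4.3 default yields where something else is specified, and SAP 4.2, just before it, does specify something else. SAP 9.1 defines baseline for change scores, not a window for counting events. Using the default for controls alone produces the unequal window.

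Finally, nothing in the documents gives risk by hour after randomization, so the pre-dosing gap cannot be called the period of highest risk. Two hours is also a maximum, not an expected loss.

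**Conclusion.** The point holds in two parts.

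1. SAP 1.2.4.1 contradicts SAP 4.2 and protocol 3.4.1 on the end of the window, and it falls 43 to 64 days short of the time point of two of its own endpoints. The rest of the SAP shows what was meant, so this is a text correction.
2. The start at lucinactant initiation, in all three passages, conflicts with the ITT population and with the randomization origin. Taken literally, it omits active-arm events for up to 2 hours after randomization and in infants never dosed. The main effect is on intubation and surfactant counts and times, with a lesser effect on worsening.

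The second part assumes that the introductory sentence of SAP 4.2 is applied as written to active infants and the SAP 4.3 default to controls. A programmer who used randomization throughout would avoid the problem, but the plan does not tell them to. Efficacy is exploratory, descriptive and untested, so no error rate, sample size or primary safety conclusion depends on this.

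**What to change.** - **SAP 1.2.4.1:** replace the Study Day 7 end with study completion. SAP 4.2 and protocol 3.4.1 already have that end and need no change to it.
- **SAP 1.2.4.1, SAP 4.2 and protocol 3.4.1:** start the window at randomization in both arms for all clinical efficacy endpoints, and state that infants randomized but not dosed are included.
- **Keep** the birth-based 72-hour and 7-day limits for the worsening categories.
- **Keep** ADS technical performance as an active-arm summary of the dosing period. A common two-arm window does not apply to it.

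The cost is one sentence in each of three places. Protocol 7.6.2 and 7.6.3 already collect intubation dates and times from randomization to the end of the study, so no new data are needed.

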1.3 HYPOTHESES

This study has no hypothesis tests.

2 INVESTIGATIONAL PLAN

2.1 STUDY POPULATION

The study population will consist of preterm neonates from 26 to 28 completed weeks PMA with RDS. This study will enroll up to 64 preterm neonates who are candidates for SRT and nCPAP in a neonatal intensive care unit (NICU) setting.

A subject will be enrolled at 1 of approximately 25 study sites in the US. It is anticipated that approximately 640 subjects will be screened to meet the enrollment goal of approximately 64 subjects (10:1 ratio of screened to enrolled).

2.1.1 Inclusion criteria

Each subject must meet all of the following inclusion criteria to be enrolled in this study:

1. Signed ICF from legally authorized representative;
2. Gestational age 26 to 28 completed weeks PMA;
3. Successful implementation of controlled nCPAP within 90 minutes after birth;
4. Spontaneous breathing;
5. Chest radiograph consistent with RDS; and
6. Within the first 20 hours after birth, requires an nCPAP of 5 to 6 cm H₂O to maintain SpO₂ of 88% to 95% with an FiO₂ of 0.25 to 0.50 that is clinically indicated for at least 30 minutes. Transient (<10 minutes) FiO₂ excursions below 0.25 or above 0.50 do not reset the 30 minute requirement.

2.1.2 Exclusion Criteria

Subjects meeting any of the following exclusion criteria may not be enrolled in this study:

1. Heart rate that cannot be stabilized above 100 beats/minutes within 5 minutes of birth;
2. Recurrent episodes of apnea occurring after the initial newborn resuscitation period (ie, 10 minutes after birth) requiring intermittent positive pressure breaths using inflating pressures above the set CPAP pressure administered manually or mechanically through any patient interface;
3. A 5-minute Apgar score < 5;

4. Major congenital malformation(s) and cranial/facial abnormalities that preclude nCPAP, diagnosed antenatally or immediately after birth;
5. Other diseases or conditions potentially interfering with cardiopulmonary function (eg, hydrops fetalis or congenital infection such as TORCH);
6. Known or suspected chromosomal abnormality or syndrome;
7. Premature rupture of membranes (PROM) > 2 weeks;
8. Evidence of hemodynamic instability requiring vasopressors or steroids for hemodynamic support and/or presumed clinical sepsis;
9. Need for endotracheal intubation and/or mechanical ventilation; and
10. Has been administered any the following:
 - a) Any investigational agent or exposure to a medical device,
 - b) Any other surfactant agent, or
 - c) Steroid treatment (steroid exposure before birth is acceptable).

2.2 STUDY DESIGN AND RANDOMIZATION

This study is a multicenter, randomized, open-label, controlled study, to evaluate the safety and tolerability of a novel investigational drug-device combination product (lucinactant for inhalation) in conjunction with nCPAP, in preterm neonates with RDS who are under the care and observation of a NICU. The study will explore escalating exposures of lucinactant for inhalation in a sequential manner through 4 unique dosing groups. All subjects randomized to the active study arm will receive the same concentration of study drug to provide the same total dose exposure for that arm. Subjects in all 4 dosing groups are eligible for a repeat dose if the repeat dosing criterion is met (see Section 2.2.2). Subjects randomized to the control arm will receive nCPAP alone.

2.2.1 Treatment Groups

Study Group	Treatment Assignment	Number of Subjects
Dosing Group I	Active Arm : 50 mg TPL/kg Delivered over 30 minutes in conjunction with nCPAP 1 repeat dose allowed if repeat dosing criterion met	n=8
	Control Arm : Continuous nCPAP	n=8
Dosing Group II	Active Arm : 75 mg TPL/kg Delivered over 45 minutes in conjunction with nCPAP 1 repeat dose allowed if repeat dosing criterion met	n=8
	Control Arm : Continuous nCPAP	n=8
Dosing Group III	Active Arm : 100 mg TPL/kg Delivered over 60 minutes in conjunction with nCPAP 1 repeat dose allowed if repeat dosing criterion met	n=8
	Control Arm : Continuous nCPAP	n=8
Dosing Group IV	Active Arm : 150 mg TPL/kg Delivered over 90 minutes in conjunction with nCPAP 1 repeat dose allowed if repeat dosing criterion met	n=8
	Control Arm : Continuous nCPAP	n=8

Note: TPL = Total Phospholipids

The study dosing will initiate in Dosing Group I at the lowest dose. Only after completion of the Safety Review Committee (SRC) review and subsequent approval, will the study progress to the next dose level for subjects in Dosing Group II. After all active subjects within each dosing group have completed assessments through 72 hours; the SRC will review the safety and tolerability of this dose. Following enrollment completion and SRC approval, dose escalation will proceed to the next dosing group.

If there appears to be intolerability with a given dose or operational challenges administering a dose, the remaining subjects may have the dose decreased to a previously administered dose, after consultation with the SRC.

The term “treatment group” will be defined as subjects in each of the active doses and the control arm subjects combined.

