- Study Duration:** Overall study enrollment will be completed in approximately 7 months, with the last subject completing their last visit approximately 9 months from the time of the first subject enrolled.
- Subject participation will be from ≤ 20 hours following birth until 36 weeks PMA or discharge, whichever comes first.
- Method of Administration:** Subjects randomized to the active study arm will be administered an investigational drug-device combination product, lucinactant for inhalation, in conjunction with nCPAP. Reconstituted lyophilized lucinactant (reconstituted with sterile water for injection) will be aerosolized by the investigational device, ADS (using the CAG), and introduced into the nCPAP circuit. Those randomized to the control arm will continue to receive nCPAP alone.
- The exposure time will be based on the nominal dose, defined as the volume of lucinactant aerosolized by the ADS. Exposure, defined as the emitted dose, is the amount of lucinactant that is delivered at the connection to the patient interface by the ADS at a constant rate of flow. Because of losses that occur as the lucinactant aerosol travels from the ADS to the patient interface, the emitted dose is approximately 35% of the nominal dose. The theoretical inhaled dose, the fraction of the aerosolized lucinactant that the infant is exposed to that is likely to be inhaled, is estimated by product of the aerosol concentration, the minute ventilation of the infant, and the administration time of the aerosol.

Dosing Groups:

- Dosing Group I Active Arm (n = 8): 50 mg TPL/kg administered over 30 minutes in conjunction with nCPAP
1 Repeat dose of 50 mg TPL/kg administered over 30 minutes is allowed if repeat dosing criteria are met.
Control Arm (n = 8): Continuous nCPAP
- Dosing Group II Active Arm (n = 8): 75 mg TPL/kg administered over 45 minutes in conjunction with nCPAP
1 Repeat dose of 75 mg TPL/kg administered over 45 minutes is allowed if repeat dosing criteria are met.
Control Arm (n = 8): Continuous nCPAP
- Dosing Group III Active Arm (n = 8): 100 mg TPL/kg administered over 60 minutes in conjunction with nCPAP
1 Repeat dose of 100 mg TPL/kg administered over 60 minutes is allowed if repeat dosing criteria are met.
Control Arm (n = 8): Continuous nCPAP
- Dosing Group IV Active Arm (n = 8): 150 mg TPL/kg administered over 90 minutes in conjunction with nCPAP
1 Repeat dose of 150 mg TPL/kg administered over 90 minutes is allowed if repeat dosing criteria are met.

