5.2.3 Method of Assigning Study Subjects to Dosing Groups

For each dosing group, preterm neonates who successfully meet all eligibility criteria within the enrollment period (20 hours) will be randomly assigned to 1 of 2 study arms (active or control) (Section 5.2.2). Subjects will be randomized using centralized allocation by an interactive web response system (IWRS). Infants from multiple births will be randomized independently.

The randomization code list will be generated by Discovery Biometrics personnel and transmitted to the IWRS vendor. The code list will use a block size of 4 for each dosing group.

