5.2.4 Sequential Dosing Scheme

The study dosing will initiate in Dosing Group I (the lowest dose), and continue to Dosing Group II after completion of enrollment. Each dosing group will enroll sequentially following completed enrollment of the previous dosing group. After all active subjects within each dosing group have completed 72 hours, the SRC will review the safety and tolerability of this dose.

If there appears to be intolerability with a given dose or operational challenges administering a dose, the remaining subjects may have the dose decreased to a previously administered dose, after consultation with the SRC.

Further details on the dosing for each dosing group are provided in Section 5.2.2.

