13.1 Statistical and Analytical Plans

The statistical analysis will be based on all randomized subjects in the study, ie, the Intent-to-Treat (ITT) population. In addition, all evaluable subjects will be analyzed for efficacy signals. Evaluable subjects are those in whom complications of prematurity (eg, PDA, IVH, sepsis,) do not preclude assessment of efficacy signals (eg, improvement in oxygenation, need for intubation and IMV). For all variables, summary statistics will be provided by dosing group, including frequency count and percentage for discrete or categorical variables, and mean, standard deviation, median, minimum, and maximum for continuous variables. In addition, time-to-event variables will be summarized using Kaplan-Meier methodology. Incidence and rates of death, BPD, survival without BPD, and worst-stage ROP at 36 weeks PMA will be summarized.

If no values are recorded in a given eCRF data field, they will be treated as missing and will not be imputed.

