13.3 Sample Size and Randomization

Sample size is not based on statistical estimation for this phase 2 study. The number of subjects randomized (approximately 8 in each active group and approximately 8 in each control group) will be considered sufficient to establish safety and tolerability before proceeding to the next higher dose. The total of approximately 32 subjects assigned to the active arm and approximately 32 subjects for the control arm for the entire study is considered sufficient to assess overall safety and tolerability.

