Dosing Group I	Active Arm : 50 mg TPL/kg Delivered over 30 minutes in conjunction with nCPAP 1 repeat dose allowed if repeat dosing criterion met	n=8
	Control Arm : Continuous nCPAP	n=8
Dosing Group II	Active Arm : 75 mg TPL/kg Delivered over 45 minutes in conjunction with nCPAP 1 repeat dose allowed if repeat dosing criterion met	n=8
	Control Arm : Continuous nCPAP	n=8
Dosing Group III	Active Arm : 100 mg TPL/kg Delivered over 60 minutes in conjunction with nCPAP 1 repeat dose allowed if repeat dosing criterion met	n=8
	Control Arm : Continuous nCPAP	n=8
Dosing Group IV	Active Arm : 150 mg TPL/kg Delivered over 90 minutes in conjunction with nCPAP 1 repeat dose allowed if repeat dosing criterion met	n=8
	Control Arm : Continuous nCPAP	n=8

Note: TPL = Total Phospholipids

Dosing Group I will complete study dosing and all active subjects will complete 72 hour safety assessments and procedures before the Safety Review Committee (SRC) review. The SRC will complete their review of all available Dosing Group I safety data (to include study-related adverse events [AEs], serious adverse events [SAEs], and additional safety endpoints) before recommending advancing enrollment to additional dosing groups. If the SRC concludes there are no safety concerns that would preclude proceeding to the next higher dose, dosing will commence in Dosing Group II. Likewise, the SRC will review the safety and tolerability of this dose and each succeeding dose, with dosing proceeding in the next dosing group if the SRC determines there are no safety concerns.

Repeat dosing will be allowed in each dosing group. Subjects meeting the repeat dosing criterion will receive an additional treatment of the same dose. Repeat dosing will be allowed between 2 and 24 hours after completion of the initial dose.

Subjects will be followed for safety evaluations (including, but not limited to, AEs and concomitant medications) until the subject is 36 weeks PMA or is discharged. Descriptive statistics (number of subjects, percent, mean, standard deviation, median, minimum, maximum) will be presented by treatment group, defined as each of the active doses (n = 8; 32 subjects total) and the all controls combined (n = 32). A final visit will occur at 36 weeks PMA or at the time of discharge or withdrawal (whichever occurs first) for all subjects.

Key safety and tolerability endpoints in the study include:

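### SAP 2.2.1 shows each 8-infant dose only beside controls pooled over four sequential cohorts, so no planned display gives a dose against its own randomized controls or shows whether control rates were stable

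*SAP*

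**What the plan says.** **Display.** SAP 2.2.1 defines treatment group as "subjects in each of the active doses and the control arm subjects combined". The SAP Executive Summary gives the sizes: "defined as each of the active doses (n = 8; 32 subjects total) and the all controls combined (n = 32". SAP 4.3 applies this to efficacy: "Summary statistics will be presented by treatment group". SAP 6.4 (adverse events), 6.4.5 (deaths) and 6.5.8 (complications of prematurity) also summarize by treatment group. No title in the SAP's list of tables, listings and figures splits controls by dosing group, and SAP 4.5 plans no subgroup summaries.

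**Design.** Protocol 13.3 plans "approximately 8 in each active group and approximately 8 in each control group". On randomization, protocol 5.2.3 says: "The code list will use a block size of 4 for each dosing group". On timing, protocol 5.2.4 says: "Each dosing group will enroll sequentially following completed enrollment of the previous dosing group". The protocol summary adds: "Overall study enrollment will be completed in approximately 7 months".

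**Protocol analysis text.** Protocol 13.1 says: "For all variables, summary statistics will be provided by dosing group". Protocol 6.1 and 13.2 say that controls are aggregated at each Safety Review Committee (SRC) review. SAP 1.3 states that there are no hypothesis tests, and SAP 6.4 says that adverse events will not be compared between treatment groups.

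**The concern.** For any one dose, the randomized comparison is with the 8 controls allocated in the same blocks over the same weeks. No planned output shows that comparison. If background event rates change between cohorts, through site mix, growing experience with the device or shifting nCPAP practice, each dose is set against an average from other periods. The change can then look like a dose effect.

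The trial's questions are largely per-dose. The primary objective compares lucinactant with nCPAP alone (protocol 3.1). The secondary objective is a maximum tolerated dose judged from safety data within each dosing group (protocol 3.2, SAP 1.2.2). SAP 1.1.2 says the results will help select doses. SAP 2.2.3 justifies the sample size by 8 active and 8 control infants per group before each escalation, yet no planned table shows those 8 controls.

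Pooling controls is reasonable if their rates are stable over the four cohorts. The planned tables give the reader no view of whether they were.

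**Working it through.** **1. The plan's own count.** 4 × 8 = 32 active and 4 × 8 = 32 control, total 64. This reproduces the stated figures.

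**2. Concurrent share.** Beside any dose, 8/32 = 25% of controls are concurrent and 24/32 = 75% are not.

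**3. Bias under drift (assumed).** The documents give no drift and no expected control rate for this trial. Suppose the background rate changes linearly by a total of D from Group I to Group IV, and the drug does nothing. The pooled control rate is the mean over cohorts, so the apparent effects for Groups I to IV are −D/2, −D/6, +D/6 and +D/2.

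| Total drift D | Group I | Group II | Group III | Group IV | All active vs all control |
|---|---|---|---|---|---|
| 10 points | −5 | −1.7 | +1.7 | +5 | 0 |
| 20 points | −10 | −3.3 | +3.3 | +10 | 0 |
| 30 points | −15 | −5 | +5 | +15 | 0 |

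Signs reverse if the rate falls. Against concurrent controls every entry is 0 in expectation. The last column is 0 because each cohort contributes equally to both arms.

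**4. Precision.** The standard error (SE) of a difference in proportions is √[p(1−p)(1/n₁ + 1/n₂)].

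| Assumed p | 8 vs 32 pooled | 8 vs 8 concurrent |
|---|---|---|
| 0.1 | 0.119 | 0.150 |
| 0.3 | 0.181 | 0.229 |
| 0.5 | 0.198 | 0.250 |

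The ratio is √[(1/8 + 1/32)/(1/8 + 1/8)] = √0.625 = 0.79 throughout.

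**5. Bias and variance together.** Root mean squared error (RMSE) of dose minus control = √(active variance + control variance + bias²). At a mean rate of 0.5, Groups I and IV are alike:

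| Total drift | RMSE pooled | RMSE concurrent |
|---|---|---|
| 10 points | 0.203 | 0.249 |
| 20 points | 0.218 | 0.245 |
| 30 points | 0.242 | 0.239 |

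For Group IV the two cross at a total drift of about 30 points (0.295 at mean rate 0.5, 0.32 at mean rate 0.3). In Group I at mean rate 0.3 they cross sooner: 0.191 pooled against 0.200 concurrent at 20 points, but 0.211 against 0.179 at 30 points.

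**6. SRC reviews.** If aggregate means all controls enrolled so far, the concurrent share at reviews 1 to 4 is 8/8, 8/16, 8/24 and 8/32, that is 100%, 50%, 33% and 25%. A 20-point drift then gives a bias of 0, 3.3, 6.7 and 10 points.

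**The case against.** The case for the SAP's layout is substantial.

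- **Pooling does not cause the confounding.** A reader might infer that the SAP discards the randomization and creates a confounding of dose with time. The documents do not support that. Sequential enrollment in protocol 5.2.4 creates the link. Figures 2.1 to 2.3 show all active against all control, which stays balanced by cohort, and the titles of Tables 6.3.5 and 6.4.1 refer to a total active group. Only the per-dose view loses its randomized comparator. This stands.
- **The protocol supports some aggregation.** A reader might infer that the SAP plainly breaks the protocol. But protocol 6.1 and 13.2 aggregate controls at SRC reviews, and 13.1 does not spell out a control column per cohort. Reading 13.1 that way is reasonable, since Table 5.2-1 places both arms inside each dosing group, but it is an inference. The 6.1 and 13.2 statements concern interim reviews and do not settle the final tables. The texts need reconciling.
- **The analysis is descriptive.** No test or error rate is affected. True, but the primary objective is comparative in wording, and columns set side by side will be read that way.
- **Drift may be small.** Planned enrollment is about 7 months, with the same entry criteria and control treatment throughout. This stands, and it is why a range is shown.
- **Pooling is usually the more accurate choice at n = 8.** This stands for modest drift (steps 4 and 5). A false 20-point trend between Groups I and IV is also smaller than one SE of an 8 versus 8 difference, 0.25 at a rate of 0.5. A reader might conclude that the pooled column should be replaced; the figures do not support that.

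**Conclusion.** The point holds as an omission in the per-dose displays. Each dose is shown only beside a control group that is 75% non-concurrent, nothing planned shows control rates by cohort, and SAP 2.2.1 and protocol 13.1 differ without explanation.

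The possible distortion is half the total drift in the first and last groups, in opposite directions: 5, 10 or 15 points for 10, 20 or 30 points. It rests on assumed linear drift, an inert drug and exactly 8:8 in each cohort. The documents neither establish nor exclude such drift. The all-active versus all-control view is unaffected.

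**What to change.** 1. Reconcile SAP 2.2.1 and the Executive Summary with protocol 13.1, stating which control group each table shows and why.
2. Keep the pooled control column. Add each dosing group's own control column (n = 8) to the key tables: worsening respiratory status, intubation, BPD, air leak, AEs and SAEs, deaths, and complications of prematurity.

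An all-active versus all-control difference stratified by dosing group is not needed, because with 8:8 in every cohort it equals the crude difference.

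**Cost.** Four extra columns in those tables and no new data, since protocol 8.2 already records each infant's dosing group assignment. The columns will be noisy: at a rate of 0.5, one has an SE of √(0.25/8) = 0.18. They can reveal a gross shift between cohorts but cannot prove stability, and a table note should say so.
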